5.13.2 POOLABILITY OF DATA

All data obtained from up to 8 sites participating in this study will be pooled into a single database for which data analysis will be performed.

Poolability is considered to be appropriate as all sites will use the same study Protocol and Appendices (such as Case Report Forms). Also, all investigational teams will

CARBOCLEAR PEDICLE SCREW SYSTEM

receive the same training by the Sponsor representative. The appropriateness of pooling data from multiple centers is necessarily enhanced by training all participating centers to follow the same protocol, with, among other things, clearly defined inclusion and exclusion criteria for study participation. Periodic monitoring visits shall be conducted to verify full understanding and fulfillment of the procedure at all sites. In addition, performance and evaluation of X-Rays images will be performed using the same means and definitions, according to written radiographic protocol, by the same independent reviewers. Likewise, independent reviewers (clinical events committee) will assess all adverse events to determine the severity of the events and their relationship to the procedure and investigational device (please refer to **Section 5.14.4**). Thus, this multi-center study includes standardization of subject enrollment, data collection and evaluation, and adverse event reporting and evaluation, with all sites following the requirements of the same Protocol.

Prior to pooling the data, the demographic information items will be reviewed to verify that their average values for all sites are within one standard deviation. Furthermore, the Company will perform poolability analyses of baseline characteristics and cage type in order to confirm the homogeneity of the entire patient population.

In particular, before combining the US and OUS data (*e.g.*, patients from US and patients from OUS in the proposed study; as well as patients from the proposed IDE study and patients from the ongoing OUS study) the baseline demographics and prognostic characteristics between the groups will be compared to evaluate the poolability of the US and OUS data. The characteristics to be compared include:

- Age
- Gender
- Pre-operative VAS
- Pre-operative ODI
- Diagnosis (DDD, Degenerative Spondylolisthesis ≤ Grade I, Spinal Stenosis < 40%, or other)
- Previous spinal surgical treatment (yes/no)
- Type of interbody fusion device used (for subjects participating in the IDE study)

These characteristics will be compared using a t-test or a Wilcoxon rank sum test for continuous variables and a Chi-square test or a Fisher's exact test for categorical variables, as appropriate. If the OUS data is similar to the US data then the data will be pooled and analyzed as a single group. If the US and OUS data are dissimilar, then the combining of the two datasets may need to be reevaluated. The reasons for dissimilarity will be investigated and the effect of investigational treatment in the presence of the disparate results will be discussed. In addition, primary analysis results stratified by US and OUS sites will be presented.

With regards to the ongoing OUS study – as described in the above Section 5.13.1, poolability of data for the statistical analysis is deemed eligible.

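### The poolability checks in 5.13.2 can pass moderate baseline differences, leave out the known treatment difference, and are settled in advance for the ongoing OUS data

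*Combined protocol and SAP*

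**What the plan says.** Section 5.13.1 plans the analysis on about 100 patients: 55 from the IDE study and about 45 from the ongoing OUS study. It states that the IDE study uses an interbody fusion device and the ongoing OUS study does not.

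Section 5.13.2 sets out three layers of checking.

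- **Sites.** Before pooling, "demographic information items will be reviewed to verify that their average values for all sites are within one standard deviation". The standard deviation is not defined.
- **Whole population.** The sponsor will "perform poolability analyses of baseline characteristics and cage type in order to confirm the homogeneity of the entire patient population". No method or limit is attached.
- **US v OUS, expressly including IDE v ongoing OUS.** Here "the baseline demographics and prognostic characteristics between the groups will be compared to evaluate the poolability of the US and OUS data". The items are age, gender, pre-operative VAS and ODI, diagnosis, previous spinal surgery, and type of interbody device, the last for IDE subjects only. The stated methods are as follows: "compared using a t-test or a Wilcoxon rank sum test for continuous variables and a Chi-square test or a Fisher's exact test for categorical variables". No significance level is given.

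The decision rule is: "If the OUS data is similar to the US data then the data will be pooled and analyzed as a single group". Otherwise: "If the US and OUS data are dissimilar, then the combining of the two datasets may need to be reevaluated", with the reasons investigated and the treatment effect discussed. Primary results will also be presented by US and OUS sites.

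The last sentence refers back to 5.13.1 and says of the ongoing OUS study that "poolability of data for the statistical analysis is deemed eligible".

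Section 5.12 calls the study a success at an overall success rate of 41%.

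**The concern.** About 45 of the 100 patients come from a separate study with a different operation, so the pooled result depends on a sound decision to combine. The stated checks give limited protection:

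- A rule tied to an undefined standard deviation cannot be applied reproducibly.
- With groups this small, failing to find a difference is weak evidence of similarity.
- The one treatment difference known in advance lies outside the compared items.
- For that same block of patients, the section both requires a check and announces its result.

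At stake is whether the pooled rate, set against 41%, describes the device as used in the IDE study.

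**Working it through.** **Inputs.** IDE 55 and ongoing OUS about 45 (5.13.1). At least 30 US patients (5.6), so at most 55 − 30 = 25 OUS patients in the IDE study, and about 25 + 45 = 70 OUS patients overall. Up to 8 sites (5.6), about 55/8 ≈ 7 patients each if all recruit. Assumed: two-sided 5% tests and a patient-level SD.

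**1. The plan's own precision figures (5.12).** Half-width = 1.96 × √(p(1−p)/n).

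- Fusion, 88%, n = 100: 1.96 × √(0.88 × 0.12/100) = 6.4 points. Reproduced.
- Safety events, 13.5%, n = 100: 1.96 × √(0.135 × 0.865/100) = 6.7 points. Reproduced.
- With the IDE study alone (n = 55) they become 8.6 and 9.0 points. That is the precision bought by pooling.

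**2. Power of the baseline tests.** For a t-test, the noncentrality is d/√(1/n1 + 1/n2), with n1 + n2 − 2 degrees of freedom. The square root is 0.201 (55 v 45), 0.271 (30 v 25) and 0.218 (30 v 70).

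| True difference | IDE 55 v ongoing OUS 45 | US 30 v OUS 25 within IDE | US 30 v all OUS 70 |
|---|---|---|---|
| 0.3 SD | 32% | 19% | 28% |
| 0.5 SD | 69% | 44% | 62% |
| 0.8 SD | 98% | 83% | 95% |
| 1.0 SD | 99.8% | 95% | 99.5% |

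The difference detectable with 80% power is (1.960 + 0.842) × the square root: 0.56, 0.76 and 0.61 SD. For a categorical item at 50% v 70%, Fisher's test has 50%, 27% and 44% power.

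**3. False alarms.** If any one significant item counted as dissimilar, identical groups would be flagged with probability 1 − 0.95^6 = 26% (six items, IDE v ongoing OUS) or 1 − 0.95^7 = 30% (seven items), treating the items as independent.

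**4. The one-SD rule.** A site mean varies about the overall mean with SE = √(1/n − 1/55) SD. For n = 7 this is 0.353. A site truly shifted by 0.5 SD passes with probability Φ((1 − 0.5)/0.353) = 92%. At 0.8 SD it passes 71% of the time and at 1.0 SD 50%. For a site of 15 the figures are 99%, 82% and 50%.

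**5. What the checks leave out.** Cage type is compared among IDE subjects only, so cage v no cage is never compared. The promised US/OUS outcome split puts up to 25 OUS patients with a cage and about 45 without one into a single OUS stratum, as worded.

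**6. Consequence for the 41% criterion (illustrative counts, not forecasts).** Take 19/55 = 34.5% success in the IDE study and 23/45 = 51.1% in the ongoing OUS study. Pooled: 42/100 = 42%. The pooled set meets 41% and the IDE study does not. The gap of 16.6 points is smaller than the 95% half-width for a difference around 41%, 1.96 × √(0.41 × 0.59 × (1/55 + 1/45)) = 19.4 points, so an outcome test could easily miss it too.

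**The case against.** **Stronger readings that the documents do not support.**

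- A reader might infer that clearly different groups will be declared similar. The table in step 2 shows otherwise: differences of 0.8 SD or more are flagged 83% to 98% of the time. The weakness is with moderate differences.
- A reader might infer that outcomes are never examined by source. Section 5.13.2 promises primary results by US and OUS, and a discussion of the treatment effect if the data disagree. Both are descriptive, and neither governs pooling.
- A reader might apply the one-SD rule to ODI and VAS and compare one SD with the 15-point and 20-mm thresholds. The rule is worded for demographic items at site level; baseline ODI and VAS are on the tested list. Those thresholds are also within-patient changes, not differences between groups.
- A reader might take non-significance as the stated definition of similar. The section gives no definition. The inference is natural because no other criterion is offered.
- A reader might conclude that the last sentence cancels the IDE v ongoing-OUS check. It may only be summarising the eligibility screening and likeness of methods in 5.13.1. The two statements conflict and need reconciling.

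**The sponsor's best substantive reply.** Section 5.13.1 argues that posterolateral fusion without a cage is a worst case for fusion, so pooling is conservative, and reports that FDA accepted the combined sample size. The second point stands as regards size, but does not say that a poolability check is unnecessary. The first concerns fusion only, while the composite also includes pain, function, neurological status, device-related serious events and reoperation. Nor do the interim OUS readings in 5.14.2 look like a worst case: 25/26 (96.2%) fused at 6 months in single-level patients, against the 88% assumed for the IDE study. Those readings are earlier, and flexion/extension motion was assessed in only part of the patients, so they do not show the opposite either. The direction is simply not established.

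**Conclusion.** The point holds in limited form. Section 5.13.2 may judge groups similar despite moderate baseline differences: power at 0.5 SD is 44% to 69%, and a seven-patient site shifted by 0.5 SD passes the site rule 92% of the time. Similar is undefined, the consequence of dissimilarity is optional, and the section contradicts itself on whether the ongoing OUS data must be checked. The known treatment difference is outside the checks, and the planned outcome split does not by its wording isolate it. The power figures assume two-sided 5% tests and the group sizes above. The site figures assume a patient-level SD and, for the seven-patient case, that all eight sites recruit. None of this shows that the sources do differ in outcome, only that the plan would not reliably reveal it.

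**What to change.** 1. Delete the one-SD rule and the last sentence of 5.13.2.
2. Report each listed baseline item as a standardised difference with 95% CI, as description and not as a pass/fail gate. The half-widths will be about ±0.39 SD (55 v 45) and ±0.53 SD (30 v 25). A cut-off such as 0.25 SD would be exceeded by chance in 21% (55 v 45) or 36% (30 v 25) of comparisons per item when groups are identical.
3. Report the primary composite and its components with 95% CIs separately for US-IDE, OUS-IDE and ongoing-OUS patients, with the IDE v ongoing-OUS difference and its CI. Do not let an outcome test decide pooling: it would be weak, and would make the primary analysis set depend on the outcome.
4. State before outcomes are reviewed that the IDE-only result (n = 55) is shown beside the pooled result against the 41% criterion, and that the pooled claim is qualified if the two disagree.

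The cost is SAP wording and one table from data already being collected. The downside is that the IDE-only estimate is less precise (fusion 88% ± 8.6 points, against ± 6.4 pooled) and that the pooled claim may need qualification.

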5.13.3 ANALYSIS POPULATIONS

Intent-to-Treat ("ITT"): All patients treated with the device.

Per-Protocol ("PP"): All patients who did not have a major protocol violation and who completed all study visits.

The primary analysis will be based upon the ITT population. Additional analyses using the PP population will also be presented in the final report.

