5.8 MISSING DATA

Incomplete information may be available for a subject for various reasons:

- Subject stopped participation in the study at its own request;
- Continuing the follow-up is not possible/subject lost to follow-up;

Subject stopped participation in the study at the Investigator's discretion.

In general, in cases where information will be available for a certain missing data point from a previous and from the next follow-up, an interpolation of the values shall be performed. Missing data from patients that were lost to follow-up will be handle by "last value carried forward" approach (*i.e.*, the last value obtained from a subject will be used for the analysis).

5.9 **PROCEDURES**

5.9.1 **PREOPERATIVE MANAGEMENT**

- a. The Investigator will select the subjects according to the inclusion and exclusion criteria, as described in Sections 5.3 and 5.4, respectively.
- b. The Investigator will be acquainted with the technique and instrumentation required for the procedure. Training will be provided by the Sponsor or its authorized representatives in accordance with the Training Protocol (**Appendix C**).
- c. The Investigator will be familiar with the Protocol of the clinical trial.
- d. Signed written Informed Consent must be obtained for all subjects.
- e. The patients shall be instructed to refrain from the use of NSAIDS for two weeks prior to surgery.
- f. All female subjects who are of child bearing age should present a negative beta-HCG blood (pregnancy) test or submit a signed statement that she is using at least one conventional contraceptive method and that to the best of her knowledge she is not pregnant. Such woman shall be informed of the risks involved in participating in the study while pregnant and cautioned to inform the study personnel if she becomes pregnant during the timeframe of the study.

Pre-procedure assessment will be conducted according to the outline provided in the Case Report Forms (CRFs) booklet.

Pre-procedure examination includes (refer also to Table 8 below):

- Demographic data
- > Full medical history, including concomitant medications

- Physical examination
- Neurological examination
- ➢ X-Ray evaluation

The results of the said examinations shall be recorded.

During the pre-operative session, the following forms shall be completed (refer also to **Table 9** below):

- > Pre-operative CRF

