The **motor evaluation** measures the muscle strength in major muscle groups (Gluteus Maximus (hip extension); Iliopsoa (hip flexion); Quadriceps (knee extension); Hamstrings (knee flexion); Anterior Tibial Group (ankle dorsiflexion); Extensor Hallucis Longus (great toe extension); Posterior Tibial (ankle plantar flexion/eversion); and Flexor Halluces (great toe flection)). Muscle strength is evaluated on a 6-point scale ranging from 0 to 5 according to the following key

describing the ability of the patient to move the lower extremities against resistance provided by the examiner:

- ▶ 0 no movement;
- ▶ 1- muscle contraction;
- > 2 lateral movement;
- ➤ 3 against gravity;
- ➤ 4 against moderate resistance;
- \blacktriangleright 5 against full resistance.

Light-touch will test **sensation** for all lumbar and sacral dermatomes in comparison to the contralateral site. The sensation shall be graded as equivalent (normal), impaired, absent, as compared to the contralateral side.

Reflexes (Patella and Achilles) are evaluated according to Bate's Reflex Scale (a 5-point scale ranging from 0 to 4) as follows:

- > 0 − no reflex;
- > 1 somewhat diminished, low normal;
- \triangleright 2 average, normal reflex;
- > 3 brisker than average;
- ➤ 4 very brisk, hyperactive.

Straight leg raising is assessed by measurement of the degree of movement required to reproduce symptoms. A positive test is considered when the patient reports worsening of pain between 30 and 70 degrees of hip passive flexion while knee is extended.

Tenderness will be evaluated by palpation of the lower spine area – lumbar paraspinal region, lumber spinous process, sacroiliac joint, and sciatic notch. Tenderness shall be graded as negative or positive (*i.e.*, palpation provokes painful sensation).

 Patient Success –

Individual patient success with respect to *safety* is defined as:

- No worsening in neurological status (motor, sensory, reflex, straight leg raising, and tenderness assessments) and no new permanent neurological deficits present for at least 2 successive visits at or beyond 6 months (out to 24 months);
- Absence of device-related serious adverse events through 24 months;
- Absence of subsequent surgical interventions at the index level through 24 months.

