5.13.4 STATISTICAL ANALYSIS OF DATA

In general, the statistics for numerical variables shall be presented as mean \pm standard deviation, median, minimum and maximum values (range), and sample size (continuous data). Categorical data will be presented as counts (numbers) and percentage of the total (rate). In addition, 95% confidence intervals will be presented for the fusion and adverse events rates. Furthermore, subgroup summary statistics will be calculated where necessary.

Where adequate, comparison between subgroups (*e.g.*, with/without mild stenosis; with/without prior discectomy) shall be presented with differences (*e.g.*, P-values). It should be noted that comparisons between subgroups are supportive analyses; these p-values will not be adjusted for multiplicity.

Adverse events (AE) data will be listed individually and summarized. Overall AE results will be presented both on a per-subject basis and per-event basis (*i.e.*, total number of subjects with each event and total number of events reported).

Results of AE seriousness and device-relatedness will be presented as well.

The report of AEs based on specific type of event will be according to the following AE terms, listed in the table below, and in accordance with FDA list of risks applicable for pedicle screw spinal systems (FDA's Executive Summary, Table 11).

ADEVERSE EVENTS
Implant Malposition
Implant Loosening
Device Breakage
Construct Disassembly
Bone Fracture
Graft Settling/Displacement
Loss of Correction
Pseudoarthrosis
Bleeding/Vascular Injury
Neurologic Injury
Back/Leg Pain (Radiculopathy)
Dural Tear/CSF Leak
Wound problems
Infection/Sepsis
Skin Irritation
Cardiac
Respiratory
Gastrointestinal
Reoperation/Revision
Death

In addition, as per the FDA recommendation, the adverse events will be further analyzed according to the Adverse Events table provided in **Section 5.14.4.2**.

Patients who withdraw from the study (following implantation of the investigational device), are lost to follow-up, or for whom data is missing, will be analyzed individually based on the information already available for the patient. In general, if sufficient data will be available for the patient based on previously gathered

information (*e.g.*, at previous follow-up sessions) or if, in cases where fusion occurs prior to withdrawal and no adverse events have been observed, the patient may be regarded as a success.

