(includes renoperative Systemic E	vents	Kelau		uie Ope	lauve		djacer	-		J wee	KS 01	any sp	nne p	loceu	ure (initial of	subsequ	ent) at the mo	lex of
Implant (Total)																		
Breakage																		
Loosening																		
Migration																		
Malposition																		
Subsidence																		
Lumbar Spinal Event Target Level (Total)																		
Spinous Process Bone Erosion																		
Spinous Process Bone Reactive Change / Sclerosis																		

	t	gery 0 harge		harge 'eek 6		ek 6 onth 3	Mon 3 to		Mor 6 to		Moi 12 te		Mor 18 te		Investiga grou		Contr Grou	
Adverse Event Category	Ι	C	Ι	С	Ι	C	Ι	C	Ι	C	Ι	C	Ι	С	#Subjects (% of xx)	Total Events	#Subjects (% of xx)	Total Events
Spinous Process Fracture																		
Facet Joint Degenerative Changes (Weishaupt)																		
Other (please specify in footnote)£																		
Lumbar Spinal Event Adjacent Contiguous Level																		
Lumbar Spinal Event Adjacent																		
Non-Contiguous Level																		
Nonoperative Control Group Event																		
Nonunion (pseudarthrosis)																		
T. 4.1	1		1			Intra	opera	tive	Even	ts	1							
Total																		
Anatomic/Technical Difficulty																		
Lumbar –Initial Surgery																		

	t	gery o harge		harge 'eek 6	Wee to Mo		Mon 3 to		Mor 6 to			nths o 18	Moi 18 te		Investiga grou		Contr Grou	
Adverse Event Category	Ι	C	Ι	С	Ι	C	Ι	C	Ι	C	Ι	C	Ι	С	#Subjects (% of xx)	Total Events	#Subjects (% of xx)	Total Events
Lumbar – Subsequent Surgery																		
Device Unable to be Implanted																		
Intraoperative Device Revision																		
Dural Tear/Leakage																		
Intraoperative Vascular Injury																		
Anesthesia, Airway, Ventilation																		
Visceral Injury																		
Intraoperative Neurologic Injury																		
Intraoperative hypotension																		
Blood transfusion																		
Excessive blood loss																		
Major allergic reaction																		
Other (please specify in footnote)																		
		P	l eriopo	erative	Syster	nic Ev	ents (Occ	l urrin	l g ≤ 6v	veeks	s of op	erati	on)				
Total					•	1				 		-				1		
Deep vein thrombosis																		

	t	gery o 1arge	to W	harge 'eek 6	Wee to Mo		Mon 3 to		Mor 6 to		Mon 12 to		Mor 18 te		Investiga grou		Contr Grou	•-

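### The per-protocol set drops patients who have already failed and then leave, and the primary set labelled ITT has no stated place for an attempted but failed implantation

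*Combined protocol and SAP*

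**What the plan says.** Section 5.13.3 names two analysis sets.

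- The set called Intent-to-Treat is "All patients treated with the device". The word treated is not defined, and the set is not tied to consent, enrolment or attempted surgery.
- The Per-Protocol set is "All patients who did not have a major protocol violation and who completed all study visits".

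Their roles are clear: "The primary analysis will be based upon the ITT population", and "Additional analyses using the PP population will also be presented in the final report".

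Three other places bear on these definitions.

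- Individual success (5.10.3 and 5.12) includes criteria that a patient can fail well before 24 months. One is "Absence of subsequent surgical interventions at the index level through 24 months". The others are no device-related serious adverse event and no neurological worsening or new permanent deficit over two successive visits from 6 months on, which the 6- and 12-month visits can already establish.
- The handling rule in 5.13.4 covers "Patients who withdraw from the study (following implantation of the investigational device), are lost to follow-up, or for whom data is missing". For withdrawals it speaks only of patients already implanted.
- The adverse event table in 5.14.4.2 has an intraoperative row, "Device Unable to be Implanted". No section says which analysis set such a patient joins or what outcome is assigned.

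Study success (5.12) is an overall success rate of 41%, with no confidence bound.

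**The concern.** A PP rule that requires every visit selects on something that happens after surgery and may be related to outcome. A patient who is revised, or who has a device-related serious adverse event, has a known final status: failure. If that patient later withdraws or dies, the rule discards a known result. It also discards a patient who missed only the 6-week visit but has complete 24-month data. The PP table would then be a poor check on the primary analysis, because a difference between the two could reflect attendance alone.

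The primary set raises a smaller question. If treated means implanted, a patient taken to surgery in whom the system could not be placed is in no denominator. For a new screw and rod system that outcome is informative. Because success is judged against a fixed 41% with no margin, a result close to the bar could turn on whether one such patient is counted.

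**Working it through.** **The plan's own figures.** No number in the plan depends on the analysis sets, and no dropout or failed-implantation rate is given. The precision statements in 5.12 do reproduce at n=100 with 1.96 × √(p(1−p)/n): p=0.88 gives 6.37 points (plan: 6.4) and p=0.135 gives 6.70 points (plan: 6.7). The 13.5% is the sum 0.4 + 1.3 + 0.1 + 10.9 + 0.8 from the table in 5.2.1.D.

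**Inputs.** n is about 100 (5.5 and 5.13.1: 55 patients plus about 45 from the ongoing study outside the US). The bar is 41% (5.12). Two counts are assumptions: x, failures who leave before completing all visits (3 to 10), and k, attempted but not achieved implantations (1 to 5).

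**PP, only failures leave.** The rate is S/(n − x), where S is the number of successes:

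- 40/100 = 40.0% becomes 40/97 = 41.2% with x=3.
- 39/100 = 39.0% becomes 39/95 = 41.1% with x=5.
- 38/100 = 38.0% becomes 38/90 = 42.2% with x=10.

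If the x patients are safety failures, the assumed 13.5% safety failure rate becomes (13.5 − x)/(100 − x): 10.8%, 8.9% and 3.9% for x = 3, 5 and 10.

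**PP, successes leave too.** If y successes also miss a visit, the PP rate is (S − y)/(n − x − y). It exceeds S/n only when y/(x + y) is below S/n. With S=39 and x=5:

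- y=3 gives 36/92 = 39.1%, just above 39.0%.
- y=4 gives 35/91 = 38.5%, below it.

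The direction therefore depends on who leaves.

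**Primary set.** If k attempted but not implanted patients are added as failures, the rate is 41/(100 + k): 40.6% for k=1, 40.2% for k=2, 39.8% for k=3 and 39.0% for k=5. The first patient costs 41.0 − 40.6 = 0.4 points. The standard error of a 41% rate at n=100 is √(0.41 × 0.59/100) = 4.9 points. With the 55 new patients alone, 23/55 = 41.8%; one added failure gives 23/56 = 41.1% and two give 23/57 = 40.4%.

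**The case against.** The strongest reply is that the primary result is largely protected. The ITT set is primary and keeps every implanted patient who is revised, has a device-related event, withdraws or dies. No section lets the PP result decide study success. That stands, and it confines the PP defect to a supportive table.

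A reader might infer that both sets inflate the success rate against the 41% bar. The documents do not support that.

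- PP also removes patients who had not failed. It further removes withdrawn patients whom 5.13.4 may credit as successes, so the net shift can go either way.
- Nothing in the plan ends follow-up after a revision, so a failure who attends every visit stays in PP.
- That the primary set omits failed implantations is an inference from an undefined word, supported by the reference to implantation in 5.13.4. A partly completed implantation could be counted either way.

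A reader might also take the adverse event row as proof that the sponsor expects failed implantations. It is one line of a table adopted on the FDA's recommendation and used only so far as it applies. Other lines, such as upper-extremity deficits, have little bearing on this study. It shows that the event can be recorded, not that it is expected. Section 5.14.2 reports no device malfunction in 47 earlier patients. That suggests few failures, although the count is of patients already implanted.

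Last, a reader might say that non-implantation is a device failure by definition. The composite in 5.12 does not list it, and the same table has a separate row for anatomic or technical difficulty. Scoring it as non-success is a recommendation on a point where the plan is silent.

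**Conclusion.** The point holds in two parts of unequal weight. The firmer part is PP: taken literally, the rule discards patients whose failure is already established and patients whose 24-month data are complete. The illustrated shifts run from 1.2 points (three failures leave) to 4.2 points (ten leave), but only if failures alone leave. The net effect is otherwise unknown in size and sign, and it does not reach the primary analysis.

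The second part is a gap in the primary definition. On the natural reading of treated, an attempted but failed implantation has no assigned set or outcome. The effect is about 0.4 points per patient at n=100, small beside a standard error of 4.9 points. It is decisive only for a result sitting on the bar, which a criterion without a confidence bound makes possible. All values of x and k are assumptions.

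**What to change.** Amend 5.13.3 before outcome data are reviewed.

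- **Per-protocol:** patients with no major protocol violation who have either a 24-month assessment or an earlier event that already meets a failure criterion of the composite. Do not require every interim visit.
- **Primary set:** all consented patients in whom implantation of the investigational device was attempted. State the outcome of a patient in whom it was not achieved: non-success in the primary analysis, with the implanted-only rate shown as a sensitivity analysis.

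The cost is a few sentences. No visit, procedure or sample size changes. The reported primary rate may fall slightly, by about 0.4 points for each such patient at n=100, and not at all if there are none.
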